8.6 Statistical Analysis of PK Parameters

A linear mixed model for analysis of variance (ANOVA) will be performed on the natural log-transformed PK parameters C_{max} and AUC_t following the morning product use session on each of Days 1, 2, 3, and 4. The model will include sequence, product, and study period as fixed effects and subject-nested-within-sequence as a random effect. Sequence will be tested using subject-nested-within-sequence as the error term for inferential purposes. Geometric least-squares means (LSM) and 95% confidence intervals (CIs) will be provided for the PK parameters of C_{max} and AUC_t by product. Geometric LSM ratio, 95% CIs of geometric LSM ratio, and p-values will be provided for the product comparisons in C_{max} and AUC_t . The comparisons of interest will include each of the products compared to each other.

The above statistical analyses will be performed using the following SAS[®] code:

```
Proc mixed data=<>;
class subject sequence period product;
model log(parameter) = sequence period product / ddfm=KR;
random subject (sequence);
lsmeans product/diff cl alpha=0.05;
estimate "Product A versus Product D" Product 1 0 0 -1/cl alpha=0.05;
estimate "Product B versus Product D" Product 0 1 0 -1/cl alpha=0.05;
```

Imperial Brands PLC
 Project No. NER01/0004
 Celerion Project No. CA35183

estimate “Product C versus Product D” Product 0 0 1 -1/cl alpha=0.05;
 estimate “Product A versus Product B” Product 1 -1 0 0/cl alpha=0.05;
 estimate “Product A versus Product C” Product 1 0 -1 0/cl alpha=0.05;
 estimate “Product B versus Product C” Product 0 1 -1 0/cl alpha=0.05;
 run;

Note: Protocol defined the study as Days 1-4 and the CRF had periods 1-4 (each have one day), respectively. Period will be used in the database and therefore in the statistical analysis.

Non-parametric analysis (Wilcoxon Signed Rank test) will be performed for the comparisons of T_{max} between each of the study products. Median difference and 95% CI of the difference will be presented for each comparison. The CI is constructed using Walsh Averages and the appropriate quantile of the Wilcoxon Signed Rank Test Statistic.

9. SUBJECTIVE MEASURES ANALYSIS

Subjective Effects Questionnaires

The Intent to Use (VAS), Urge to Smoke (VAS), and Product Evaluation Scale (7-point scale) questionnaires will be completed using a computerised tablet device. All relevant software specific to the electronic questionnaires will be provided by IVRCC ePro.

Subjects will be familiarised with the questionnaires on Day -1. An explanation of how the questionnaires will be administered to the subjects will be given. Responses will not be recorded.

All questionnaires will be completed at the time points delineated below. When scheduled at the same time as a PK blood draw, the Urge to Smoke questionnaire will be completed approximately 30 seconds prior to the scheduled blood draw (except for the one scheduled at Time 0, which will be performed approximately 10 minutes prior to the start of the product use session), and all other questionnaires will be completed within approximately 2 minutes after the last scheduled blood draw.

9.1 Urge to Smoke (UTS)

Urge to Smoke questionnaire will be completed at Time 0 (pre-product use) and at 4, 8, 15, 45, 60, 120, and 240 minutes relative to the start of product use on Days 1, 2, 3, and 4.

The following parameters will be calculated for the urge to smoke assessments:

Emax The maximum change from baseline VAS score
 (VASpre-use - VASpost-use)

Imperial Brands PLC
 Project No. NER01/0004
 Celerion Project No. CA35183

TEmax Time of the Emax. If the maximum value occurs at more than one time point, TEmax will be defined as the first time point with this value.

AUEC₀₋₂₄₀ The area under the change from baseline VAS score versus time curve from time 0 to 240 minutes.

Baseline is the pre-product-use for each product use. Responses, change from baseline, and derived parameters will be listed by subject and summarised by product, by sex and overall using descriptive statistics, including n, mean, SD, CV%, SEM, minimum, Q1, median, Q3, maximum, and 95% CI.

An appropriate statistical method, similar to the PK analysis detailed above, will be used to compare Urge to Smoke parameters (no data transformation). LSM and 95% CIs will be provided for the E_{max} and AUEC₀₋₂₄₀ by product. LSM difference, 95% CIs of LSM difference, and p-values will be provided for the product comparisons in E_{max} and AUEC₀₋₂₄₀. The comparisons of interest will include each of the products compared to each other.

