7.3.2 Subjective Effects

7.3.2.1 Urge to Smoke Parameters

The following parameters will be calculated for the urge to smoke assessments:

E_{max} The maximum change from baseline VAS score ($VA_{Spree-use} - VA_{SpPost-use}$).

$T_{E_{max}}$ Time of the E_{max} . If the maximum value occurs at more than one time point, $T_{E_{max}}$ will be defined as the first time point with this value.

AUC_{0-240} The area under the change from baseline VAS score versus time curve from time 0 to 240 minutes.

Responses and derived parameters will be listed by subject and summarised by study product, by sex and overall using descriptive statistics.

An appropriate statistical method, similar to the PK analysis detailed above, will be used to compare Urge to Smoke parameters (no data transformation).

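### Urge-to-Smoke Emax and AUEC0-240 are compared as raw changes from each day's pre-use VAS, without that baseline as a covariate, so its day-to-day noise stays in every product contrast

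*SAP*

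**What the plan says.** SAP 9.1 builds Emax from the difference "VASpre-use - VASpost-use" and defines AUEC0-240 as "The area under the change from baseline VAS score versus time curve from time 0 to 240 minutes". It adds: "Baseline is the pre-product-use for each product use". The introduction to SAP 9 places this one reading before use, "which will be performed approximately 10 minutes prior to the start of the product use session".

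For inference SAP 9.1 states: "An appropriate statistical method, similar to the PK analysis detailed above, will be used to compare Urge to Smoke parameters (no data transformation". Protocol 7.3.2.1 also plans a method "similar to the PK analysis detailed above, will be used to compare Urge to Smoke parameters". The PK analysis in SAP 8.6 reads "The model will include sequence, product, and study period as fixed effects and subject-nested-within-sequence as a random effect", with the code line "model log(parameter) = sequence period product / ddfm=KR". The footnotes of the shells for Tables 14.2.3.1.4 and 14.2.3.1.5 repeat those terms for Urge to Smoke and list nothing more.

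Neither document plans a baseline covariate, a subject-mean baseline term or a baseline-adjusted sensitivity analysis for these parameters. LS mean differences, 95% CIs and p-values are planned for all six product pairs on both.

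**The concern.** One VAS reading per day enters Emax with weight 1 and is subtracted from every post-use point in AUEC0-240, so its total weight there is close to 240 minutes. An unusually high or low reading that morning shifts the whole result for the product used that day. Emax also cannot exceed the pre-use score, because the scale starts at zero urge (Protocol Appendix 2).

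The crossover does not remove this. The random subject effect takes out what is constant across a subject's four days, not the day-to-day part. The design leaves room for such variation: own-brand smoking is free after each *ad libitum* session, and the 12 hours of abstinence is a minimum.

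Reduction in smoking urge is secondary objective 2, and 24 subjects were chosen without statistical considerations (SAP 4). Avoidable noise means wider intervals than the data require.

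**Working it through.** **No figure to reproduce.** The documents state no power, effect size, VAS SD or correlation for Urge to Smoke. The only fixed inputs are 24 subjects, four periods, the sequences ABCD, BDAC, CADB and DCBA, Urge-to-Smoke times of 0, 4, 8, 15, 45, 60, 120 and 240 minutes, and two-sided 95% intervals. All SDs, correlations and effects below are assumptions.

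**Analytic comparison.** Let s be the within-subject SD of a VAS score on one day, and r the within-subject correlation of pre-use and post-use scores on the same day.

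- Residual variance of the change score: 2s²(1−r)
- Residual variance with the day's baseline as covariate: s²(1−r²)
- Ratio, adjusted to unadjusted: s²(1−r)(1+r) / [2s²(1−r)] = (1+r)/2
- SE of a product difference: residual SD × √(2/24)

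Illustration with s = 15 mm and a true difference of 10 mm (normal-approximation power):

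| r | Variance ratio | CI width ratio | SE planned → adjusted (mm) | Power planned → adjusted |
|---|---|---|---|---|
| 0 | 0.50 | 0.71 | 6.12 → 4.33 | 37% → 64% |
| 0.3 | 0.65 | 0.81 | 5.12 → 4.13 | 50% → 68% |
| 0.5 | 0.75 | 0.87 | 4.33 → 3.75 | 64% → 76% |
| 0.7 | 0.85 | 0.92 | 3.35 → 3.09 | 85% → 90% |
| 0.9 | 0.95 | 0.97 | 1.94 → 1.89 | above 99% for both |

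The two ratio columns do not depend on s; the SE and power columns do.

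**Simulation of the actual parameters.** Emax is a maximum over seven readings and AUEC a weighted average, so the formula is only a guide. The design was simulated with 600 trials per scenario, subject effects fixed, and scores limited to 0–100. Assumed values were mean pre-use score 70 and between-subject SD 15. Residual degrees of freedom were 96−24−3−3 = 66 without the covariate and 65 with it. Here r is the shared day variance divided by the sum of shared day and single-reading variance.

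| Shared day SD / reading SD | r | SE ratio, Emax | SE ratio, AUEC0-240 | Mean Emax A−D, planned / adjusted |
|---|---|---|---|---|
| 0 / 12 | 0 | 0.58 | 0.46 | −7.20 / −6.87 |
| 8 / 12 | 0.31 | 0.74 | 0.69 | −6.91 / −6.79 |
| 12 / 8 | 0.69 | 0.90 | 0.89 | −7.30 / −7.23 |
| 15 / 5 | 0.90 | 0.98 | 0.98 | −7.42 / −7.43 |

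At low r the gain exceeds the formula. Emax and AUEC summarise several post-use readings, so the single pre-use reading carries a larger share of the noise. The mean contrasts agree closely. The largest gap, 0.33 at r = 0, is small against a planned SE of 4.02.

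**Second set of assumptions.** With between-subject SD 18, day SD 12, measurement SD 6 and a pre/post correlation of the day effects of 0.2, 0.5 or 0.8, repeated simulations under differing product effects gave A−D variance ratios of:

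- Emax: 0.55–0.58, 0.63–0.68 and 0.73–0.79
- AUEC0-240: 0.56–0.58, 0.65–0.70 and 0.76–0.81

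Measurement error dilutes that day correlation by 12²/(12²+6²) = 144/180 = 0.8, so the r in the formula is 0.16, 0.40 and 0.64. The formula then gives 0.58, 0.70 and 0.82, in line with the simulations.

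**The case against.** The planned analysis is valid. A change from the period's own baseline, with period and product fixed and subject random, is unbiased in a randomised crossover. Chance imbalance in pre-use urge averages to zero and is already reflected in the planned SE. This stands: the issue is efficiency only.

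The benefit depends on assumptions, which also stands. With measurement SD cut to 3, the variance ratios rose to 0.85 (Emax) and 0.89 (AUEC) at day correlation 0.8. At day correlation 0.95 the gain was only about 2% to 7%. Abstinence, standardised meals and the within-subject design all limit pre-use variation. No decision rule hangs on these secondary endpoints.

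A single common slope does not fully deal with the floor. With an assumed strong product D (reduction 70, against 30 for A), within-subject Emax slopes were 0.55 for A and 1.01 for D at day correlation 0.5, and 0.33 and 0.83 at 0.8. Average precision still improved, but the model is then misspecified, so a slope check is needed.

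The summary of pre-use VAS by product in Table 14.2.3.1.1 would show an imbalance but would not correct the comparison. None of these points shows harm from the covariate: in no simulated case did it worsen precision.

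**Conclusion.** The concern holds. As written, the Urge-to-Smoke comparisons keep day-specific pre-use variation that the trial already measures and could adjust for. Relative to a baseline-adjusted analysis, the contrast variance is 2/(1+r) times as large: 2.0 times at r = 0, 1.33 times at r = 0.5 and 1.05 times at r = 0.9, assuming equal pre-use and post-use within-subject variances. The loss is substantial if r is 0.5 or less and minor near 0.9. The documents do not settle which applies.

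The cost is wider intervals and lower power on a secondary objective, with no material bias and no type I error inflation. Each baseline precedes that day's product. Across the four sequences every ordered pair of neighbouring products occurs once, so any residue of the previous day's product is spread evenly. The change should be made because it is nearly free, not because the planned analysis is invalid.

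**What to change.** In SAP 9.1, replace the reference to a similar method with an explicit model for Emax and AUEC0-240:

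- **Terms:** sequence, period and product fixed; subject within sequence random; plus that period's pre-use VAS and the subject's mean pre-use VAS over periods. The subject mean keeps within-subject and between-subject slopes apart.
- **Reporting:** LS means at the overall mean pre-use VAS, with differences and 95% CIs for the six pairs as planned.
- **Sensitivity:** the unadjusted model as now written, and a product-by-baseline term to check the common slope, chiefly for Emax near the floor.
- **Consistency:** matching PROC MIXED code, revised footnotes for the Urge-to-Smoke statistical tables, and an entry in SAP 13.

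The cost is SAP wording, two covariates in an existing procedure call and one or two degrees of freedom. The pre-use VAS is already collected on all four days. Protocol section 7 lets the SAP modify planned analyses and requires a protocol amendment only for major changes to the primary endpoints or their analysis, so a SAP revision is enough.

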9.2 Product Evaluation Scale (PES)

Intent to Use questionnaire will be completed at 240 minutes following the start of study product use on each of Days 1, 2, 3, and 4.

Product Evaluation will be considered as a 7-point scale. Responses will be presented as the following factor scores:

- a) Satisfaction: average of the response scores from questions 1, 2, 3, and 12;
- b) Psychological reward: average of the response scores from questions 4 to 8;
- c) Aversion: average of the response scores from questions 9, 10, 16, and 18;
- d) Relief: average of items 11, 13, 14, 15, and reversed for item 20 (i.e., not at all = 7, extremely = 1);
- e) Items 17, 19, 21 will be summarised as individual item scores.

Descriptive statistics of the factor scores will be provided by product, by sex and overall. Individual responses will be listed by subject.

9.3 Intent to Use (ITU)

Intent to Use questionnaire will be completed at 240 minutes following the start of study product use on each of Days 1, 2, 3, and 4.

Ratings of the subjects' 'If available, how likely are you to buy your assigned study product in the future?' recorded on a 100 mm VAS scale ranging from "Not at all" (0) to "Extremely" (100) will be reported.

Imperial Brands PLC
 Project No. NER01/0004
 Celerion Project No. CA35183

In addition, responses to ITU questionnaire will also be treated as a bipolar variable. The bipolar score will be calculated by subtracting 50 from the original VAS score, then categorizing into three categories: -50 to < 0, 0, and > 0 to 50.

Descriptive statistics of the VAS raw score and bipolar score will be provided by product. Individual responses will be listed by subject. Frequency count table will be presented for the categories of the bipolar scores.

10. PUFF TOPOGRAPHY

On Days 3 and 4 only, puff topography measurements will be performed for 2 hours during the last 2 hours of the 4-hour *ad libitum* product use session. The topography session will span a 2-hour period and the SPA-M topography device will be stopped and restarted with each new stick or cigarette during that time.

The topography parameters listed in [Table 10.1](#) and [Table 10.2](#) will be assessed:

Table 10.1 Human Puffing Topography Parameters Per-Puff

Description	Variable	Unit
Puff number	Ni	
Puff duration	Di	s
Puff volume	Vi	mL
Peak puff flow rate	Qci	mL/s
Average puff flow rate	Qmi	mL/s
Inter-puff interval	Ii	s

Imperial Brands PLC
 Project No. NER01/0004
 Celerion Project No. CA35183

Table 10.2 Human Puffing Topography Parameters Per-Product Use Experience

Description	Variable	Formula	Unit
Total number of puffs	NPC	$\sum N_i$	
Total puff volume	TVOL	$\sum V_i$	mL
Average puff volume	AvgV _i	$\sum V_i / NPC, i=1 \dots NPC$	mL
Average puff duration	AvgD _i	$\sum D_i / NPC, i=1 \dots NPC$	s
Total puff duration	TD _i	$\sum D_i$	s
Average flow rate	AvgQm _i	$\sum Qm_i / NPC, i=1 \dots NPC$	mL/s
Average peak flow rate	AvgQc _i	$\sum Qc_i / NPC, i=1 \dots NPC$	mL/s
Total inter puff interval	TI _i	$\sum I_i$	s
Average inter puff interval	AvgI _i	$\sum Qc_i / NPC, i=1 \dots NPC$	s

Topography parameters will be listed by subject and summarised by product, sex, and overall using descriptive statistics, including n, mean, SD, CV%, SEM, minimum, Q1, median, Q3, maximum, and 95% CI.

An appropriate statistical method, similar to the PK analysis detailed above, will be used to compare per product topography parameters (no data transformation). LSM and 95% CIs will be provided for the topography parameters by product. LSM difference, 95% CIs of LSM difference, and p values will be provided for the product comparisons in topography parameters. The comparisons of interest will include each of the products compared to each other.

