5.1.1 Usual Brand Combustible Cigarette

Subjects will be required to bring with them to the CRU a sufficient supply (i.e., 5-day supply [unopened packs]) of their OBCCs for personal use throughout confinement.

5.1.2 [REDACTED] HT Device with Stick

[REDACTED] works by the user inserting a specially designed consumable ([REDACTED]) into the handheld device which contains an electronically controlled heater ([Figure 2](#)). The handheld device heats the tobacco using an electronically controlled heating rod. The rod can be set to 2 temperatures: Eco mode (315°C) or Standard mode (345°C). The handheld device supplies heat to the tobacco using the heating rod for 4 minutes. The heating device must be recharged after 20 consecutive uses.

The inclusion of a foil wrap around the tobacco portion of the rod prevents the [REDACTED] stick from being lit and combusted like a CC ([Figure 3](#)).

Figure 2. Heated Tobacco Product Diagram

[figure not shown]
A

B

Figure 1A. [REDACTED] device features; Figure 1B. Assembly of the [REDACTED] device

Figure 3. ■ Stick Assembly

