2. OBJECTIVES AND ENDPOINTS

2.1 Objectives

Primary

1. To evaluate and compare the C_{max} and AUC_t of nicotine after the use of each Heated Tobacco (HT) product or combustible cigarettes (CCs) comparator.

Secondary

1. To evaluate other pharmacokinetic (PK) parameters of nicotine after the use of each HT product or CCs comparator.
2. To evaluate the reduction in smoking urges observed after the use of each HT product or CCs comparator.
3. To evaluate product perception and preference by use of subjective assessments.
4. To evaluate the tolerability and safety of each of the products used.
5. To investigate usage behaviour for each product using measurements of topography parameters (puff count, puff duration, puff volume, peak puff flow rate, average puff flow rate, inter puff interval) for each product.

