E_{max} = Maximum value of the differences (VASpre-use - VASpost-use)

Program: /CAXXXX/sas_prg/pksas/PROGRAMNAME.SAS DDMMYY HH:MM

Programming Note: Summaries for Female and Overall will also be included in the table. Parameters include Emax, AUEC0-240.

Statistical Analysis Plan, 13 January 2022

Imperial Brands PLC
 Project No. NER01/0004
 Celerion Project No. CA35183

Note: Statistical summary table of Urges to Smoke Parameters by product (Table 14.2.3.1.4) and Puff Topography 14.2.4.2) will have the following format:

Table 14.2.3.5 Statistical Summary of Urge to Smoke Parameters Emax and AUEC0-240 Follow Use (Outcomes Population)

Product	Parameter	n	----- LS Mean -----	95% Confidence Interval
A	Emax	X	X.XX	XX.XX - XXX.XX
	AUEC0-240	X	X.XX	XX.XX - XXX.XX
B	Emax	X	X.XX	XX.XX - XXX.XX
	AUEC0-240	X	X.XX	XX.XX - XXX.XX
C	Emax	X	X.XX	XX.XX - XXX.XX
	AUEC0-240	X	X.XX	XX.XX - XXX.XX
D	Emax	X	X.XX	XX.XX - XXX.XX
	AUEC0-240	X	X.XX	XX.XX - XXX.XX

Product A: < >

Product B: < >

Product C: < >

Product D: < >

n = Number of observation used in the analysis

The mixed model includes sequence, product, and study period as fixed effects and subject effect. Mixed model with a default (variance component) covariance structure was used.

Least-squares means (LS Means) are calculated from the ANOVA.

Program: /CAXXXXX/sas_prg/pksas PROGRAMNAME.SAS DDMMYYYY HH:MM

Programmer Note: Refer to Table 10-2 for the list of topography parameters.

Statistical Analysis Plan, 13 January 2022

Imperial Brands PLC
 Project No. NER01/0004
 Celerion Project No. CA35183

Note: Statistical comparison table of Urges to Smoke Parameters (Table 14.2.3.1.5) and Puff Topography Parameters have the following format:

Tables 14.2.3.1.5 Statistical Comparison of Urge to Smoke Parameters Emax and AUEC0-240 (Outcomes Population)

Comparison	Parameter	LS Means		LS Mean Difference (Test - Reference)
		Test (n)	Reference (n)	
Product A vs Product D	Emax AUEC0-240	X.XX (X) X.XX (X)	X.XX (X) X.XX (X)	XXX.XXXX.XX - XX XXX.XXXX.XX - XX
Product B vs Product D	Emax AUEC0-240	X.XX (X) X.XX (X)	X.XX (X) X.XX (X)	XXX.XXXX.XX - XX XXX.XXXX.XX - XX
Product C vs Product D	Emax AUEC0-240	X.XX (X) X.XX (X)	X.XX (X) X.XX (X)	XXX.XXXX.XX - XX XXX.XXXX.XX - XX
Product A vs Product B	Emax AUEC0-240	X.XX (X) X.XX (X)	X.XX (X) X.XX (X)	XXX.XXXX.XX - XX XXX.XXXX.XX - XX
Product A vs Product C	Emax AUEC0-240	X.XX (X) X.XX (X)	X.XX (X) X.XX (X)	XXX.XXXX.XX - XX XXX.XXXX.XX - XX

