Product B vs Product C	Emax AUEC0-240	X.XX (X) X.XX (X)	X.XX (X) X.XX (X)	XXX.XXXX.XX - XX XXX.XXXX.XX - XX

Test = The first product in the comparison

Reference = The second product in the comparison

n = Number of observation used in the analysis

Product A: < >

Product B: < >

Product C: < >

Product D: < >

The mixed model includes sequence, product, and study period as fixed effects and subject nested as random effects.

Mixed model with a default (variance component) covariance structure was used.

Least-squares means (LS Means) are calculated from the ANOVA.

Program: /CAXXXXX/sas_prg/pksas PROGRAMNAME.SAS DDMMYYYY HH:MM

Programmer Note: Refer to Table 10.2 for the list of topography parameters.

Statistical Analysis Plan, 13 January 2022

Imperial Brands PLC
 Project No. NER01/0004
 Celerion Project No. CA35183

Note: Subjective measure tables for PES factor scores (14.2.3.2) will have the following format.

Table 14.2.3.2 Summary of PES Factor Scores by Study Product for Controlled Product Use (Outc

Subscale	Sex	Statistics	Product A	Product B	Product C
Satisfaction	Male	n	X	X	X
		n missing	X	X	X
		Mean	X.X	X.X	X.X
		SD	X.XX	X.XX	X.XX
		CV (%)	XX.X	XX.X	XX.X
		SEM	X.XX	X.XX	X.XX
		Minimum	XX	XX	XX
		Q1	X.X	X.X	X.X
		Median	X.X	X.X	X.X
		Q3	X.X	X.X	X.X
		Maximum	XX	XX	XX
		95% CI	X.X-X.X	X.X-X.X	X.X-X.X

Product A: < >
 Product B: < >
 Product C: < >
 Product D: < >

Program: /CAXXXX/sas_prg/pksas/PROGRAMNAME.SAS DDMMYYYY HH:MM

Programming Note: Summaries for Female and Overall will also be included in the table. Subscales includes Satisfaction, Reward, Aversion, Relief, and single items 17, 19, and 21.

Statistical Analysis Plan, 13 January 2022

Imperial Brands PLC
 Project No. NER01/0004
 Celerion Project No. CA35183

Note: Subjective measure tables for Intent to Use VAS Scores (14.2.3.3.1 through 14.2.3.3.3) will have the following

Table 14.2.3.3.1 Frequency of Responses to Future Intent to Use in Each Category by Study Product Use (Outcomes Population)

Product	Sex	Use the Product Again Response			Category
		-50 to <0	<0	>0 to 50	
A	Male	n (%)	XX (XX%)	XX (XX%)	XX (XX%)
	Female	n (%)	XX (XX%)	XX (XX%)	XX (XX%)
	Overall	n (%)	XX (XX%)	XX (XX%)	XX (XX%)
B	Male	n (%)	XX (XX%)	XX (XX%)	XX (XX%)
	Female	n (%)	XX (XX%)	XX (XX%)	XX (XX%)
	Overall	n (%)	XX (XX%)	XX (XX%)	XX (XX%)
C	Male	n (%)	XX (XX%)	XX (XX%)	XX (XX%)
	Female	n (%)	XX (XX%)	XX (XX%)	XX (XX%)
	Overall	n (%)	XX (XX%)	XX (XX%)	XX (XX%)
D	Male	n (%)	XX (XX%)	XX (XX%)	XX (XX%)

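### SAP Table 10.2 defines average inter-puff interval with the formula for average peak flow rate, so that row would report a flow labelled in seconds

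*SAP*

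**What the plan says.** SAP section 10 has two topography tables. Table 10.1 lists the per-puff variables. Among them are "Peak puff flow rate", Qc_i, in mL/s, and the inter-puff interval, I_i, in s. Table 10.2 derives nine per-product parameters from them. Three of its rows matter here:

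- "Average peak flow rate": ΣQc_i / NPC, in mL/s
- "Total inter puff interval": ΣI_i, in s
- "Average inter puff interval": ΣQc_i / NPC, in s

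The text below the table has the per-product parameters compared between all pairs of products on the untransformed scale, with LS means, LS mean differences, 95% confidence intervals and p-values. The shells in SAP 15.2 send the programmer back to this table. The statistical summary shell says "Programmer Note: Refer to Table 10-2 for the list of topography parameters" and the comparison shell says "Programmer Note: Refer to Table 10.2 for the list of topography parameters". The descriptive shell (Table 14.2.4.1) carries a similar note.

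Secondary objective 5, in both Protocol 2.1 and SAP 2.1, names the topography measures, ending with "peak puff flow rate, average puff flow rate, inter puff interval".

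**The concern.** One expression cannot be both a mean flow and a mean time. The numerator in the average interval row belongs to a different variable, so the result carries mL/s under a heading of seconds. Nothing elsewhere in the SAP supplies the right formula, and SAP section 13, which lists departures from the protocol, does not mention this row.

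At stake is a measure named in a secondary objective and tested between products. Followed literally, the SAP would never report the mean interval. A second copy of the peak-flow results would stand in its place, with p-values that a reader would take as evidence about puff spacing. The reported average would also disagree with the reported total interval in the row above.

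**Working it through.** **1. Each Table 10.2 row against its Table 10.1 variable.**

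| Row | Formula | Unit the formula yields | Unit printed |
|---|---|---|---|
| Total puffs | ΣN_i | count | none |
| Total volume | ΣV_i | mL | mL |
| Average volume | ΣV_i / NPC | mL | mL |
| Average duration | ΣD_i / NPC | s | s |
| Total duration | ΣD_i | s | s |
| Average flow | ΣQm_i / NPC | mL/s | mL/s |
| Average peak flow | ΣQc_i / NPC | mL/s | mL/s |
| Total interval | ΣI_i | s | s |
| Average interval | ΣQc_i / NPC | **mL/s** | **s** |

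Four of the five average rows use their own variable. Only the last does not, and it is the only row whose formula and unit clash.

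**2. Consequence.** The two formulas are identical, so the two parameters are equal for every record whatever the data. Every statistic computed from them is then equal too. SAP 8.6, applied in SAP 10, gives 4 product LS means and 4 × 3 / 2 = 6 pairwise contrasts. All of these, with their intervals and p-values, would repeat.

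Topography is measured on Days 3 and 4 only, so I checked that all six contrasts can be estimated. The sequences ABCD, BDAC, CADB and DCBA give the Day 3/Day 4 pairs CD, AC, DB and BA. These link all four products in a closed loop, so all six contrasts are estimable.

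**3. Illustration, with assumed values that are not from the documents.** Take one stick with 8 puffs and 7 intervals.

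- Peak flows 45, 50, 48, 42, 40, 44, 41, 38 mL/s: sum 348, and 348 / 8 = 43.5.
- Intervals 22, 25, 28, 30, 26, 31, 27 s: sum 189.
- Average interval as the SAP has it: 348 / 8 = 43.5, labelled s.
- Mean of the intervals: 189 / 7 = 27.0 s.

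**4. The divisor in a corrected formula.** Replacing Qc_i with I_i and keeping NPC may not be enough. The device is stopped and restarted for each stick or cigarette, so n puffs may give only n − 1 intervals. In the example, 189 / 8 = 23.6 s against 27.0 s. In general (n − 1)/n falls short by 1/n. Pooling k sticks with equal n changes nothing, because k(n − 1)/(kn) = (n − 1)/n.

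The documents give no ad libitum puff count. A rough anchor is the HT heating time in Protocol 5.1.2 ("The handheld device supplies heat to the tobacco using the heating rod for 4 minutes") with the 30-second spacing of the controlled session: 240 / 30 = 8 puffs.

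| Assumed n | Understatement 1/n |
|---|---|
| 6 | 16.7% |
| 8 | 12.5% |
| 10 | 10.0% |
| 14 | 7.1% |

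If the device export gives an interval for every puff, the understatement is 0%. The documents do not describe the export.

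**The case against.** The strongest reply is that this is a self-evident slip. The row label, the variable name AvgI_i, the unit and the correct total row directly above all show what was meant. A programmer would have to follow the one wrong element against all of these, and then overlook two identical sets of results. The shell notes cite Table 10.2 for its list of parameters, not expressly for its formulas. The objective names the interval, not its average. Because the per-puff intervals and their total are correctly defined, listed or summarised, the average can be recovered. Protocol 6.4.3 also allows topography to be omitted for some or all subjects, so exposure may be smaller than planned.

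Most of this is fair, and it limits the seriousness. It does not make the formula right. Table 10.2 is the only place where the derivation is given, and a correct output should not depend on someone departing from the written specification.

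A second reply is that the divisor range in step 4 concerns a formula the SAP does not contain. It also borrows controlled-use pacing for an ad libitum session, and an HT heating time that does not apply to own-brand cigarettes. Counting a puff at both 0 and 240 s would give 9 puffs (1/9 = 11.1%) instead of 8. This too is fair. The range is conditional and plays no part in establishing the error. It serves only to show why the correction should name its divisor.

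**Conclusion.** The formula is wrong as written and should be fixed. If followed, it replaces one of nine per-product topography parameters with an exact copy of another, mislabelled in seconds, in the descriptive, LS mean and comparison tables. The duplication is exact and needs no assumption about the data. It does depend on the formula being programmed literally, which is possible but not certain. It also depends on the printed symbol being what the sponsor's own SAP file contains, which is worth a glance because equation symbols can be corrupted in a PDF.

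The effect stays within one secondary measure. Cmax, AUCt, safety and the recorded topography data are not affected.

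A lesser point belongs in the same edit. NPC is printed as ΣN_i, with N_i labelled as puff number. If N_i were a running index, its sum would not be a count. The row label and the index limit NPC show that the count is meant, so this is ambiguous notation, not a demonstrated error.

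**What to change.** In SAP Table 10.2:

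1. Replace the average interval formula with ΣI_i divided by the number of recorded inter-puff intervals. This is right whether or not the device records an interval for every puff.
2. State that NPC is the count of recorded puffs.
3. Add a programming check that the average interval multiplied by the number of recorded intervals equals the total interval.

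The cost is one corrected formula, one clarified definition and one check. The values derive from per-puff data already being recorded, so nothing changes in data collection.
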